To determine the extent by which these problems affect daily life for the individual, we are including the Activity of Daily Living (ADL) questionnaire. This survey assesses standard areas of daily living to determine the number as well as the severity of the problem. This survey was designed such that patients with cognitive decline could still yield meaningful responses. This test determined normative values based on comparing a patient's baseline status to their overall score on the survey, which allows it to be sensitive to mild decline as well as severe decline in cognitive function. The test is scored by taking the total score of a patient and dividing by the number of items rated which allows the test to only measure deficits seen with activities that the patient regularly participates in. This test has a validated cut off points for determine positive results: 0-33% may indicate some impairment, 34-66% moderate impairment, 67+%: severe impairment.

Lumosity administered assessments:

1. Arithmetic Reasoning
2. Forward Memory Span
3. Reverse Memory Span
4. Digit Symbol Coding
5. Divided Visual Attention
6. Trail Making A
7. Trail Making B
8. Progressive Matrices

Then, randomization will occur to a treatment group, which will include online access to structure-oriented activities(Lumosity), and an active control group(online crosswords).

Intervention group: Participants assigned to the intervention/experimental group will undergo twenty training sessions over 10 weeks. In each session, they practice video games selected from Lumosity(<http://www.lumosity.com>), a web-based cognitive training platform that includes games designed with the purpose of improving the user's cognitive abilities (Stenberg et al., 2013). Games will be customized using an automated algorithm supplied by Lumosity, to determine performance in the various targeted skills, which include: task switching, logical reasoning, quantitative reasoning, response inhibition, numerical calculation, working memory, face-name recall, selective attention, spatial recall, spatial orientations, planning, and divided attention.

Game Name	Targeted Skill
Brain Shift	Task Switching
Brain Shift Overdrive	Task Switching
By the Rules	Logical Reasoning
Chalkboard Challenge	Quantitative Reasoning
Color Match	Response Inhibition
Disconnection	Task Switching
Disillusion	Task Switching
Division Storm	Numerical Calculation
Ebb and Flow	Task Switching
Face Memory Workout	Working Memory

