Familiar Faces	Face-Name Recall
Follow that Frog	Working Memory
Lost in Migration	Selective Attention
Memory Lane	Working Memory
Memory Match	Working Memory
Memory Match Overdrive	Working Memory
Memory Matrix	Spatial Recall
Moneycomb	Spatial Recall
Monster Garden	Working Memory
Pet Detective	Planning
Pinball Recall	Working Memory
Playing Koi	Divided Attention
Raindrops	Numerical Calculation
Rhyme Workout	Working Memory

River Ranger	Information Processing
Rotation Matrix	Working Memory
Route to Sprout	Planning
Star Search	Selective Attention
Tidal Treasures	Working Memory
Train of Thought	Divided Attention
Trouble Brewing	Divided Attention
Word Sort	Logical Reasoning

Lumosity has the ability to customize games based on the performance in five different cognitive domains. Based on the participants' performance on exercises testing speed, memory, attention, flexibility and problem solving, certain online games can be emphasized based on the needs of the patient. Of interest will also be the profile of cognitive deficits determined by the Lumosity screening process that may characterize the cognitive problems typically seen in patients with ruptured cerebral aneurysms. Based on prior literature, we will be focusing on games designed to improve divided attention, flexibility, problem solving and memory

The recommended interaction would be 2 hours per week for 10 weeks for a total training time of 20 hours over the course of the study.

Active control group: The attention control group uses a computerized crossword puzzle game. This game offers a choice between three puzzle sizes, three levels of complexity, and varying font sizes. It also includes optional help features such as filling in an unknown letter or word. There is, however, no progressive challenge to the user by either increased speed, visual field size, number of distractors, or degree of difficulty of target stimulus differentiation. Thus, the crossword puzzle program provides an appropriate, computerized attention control alternative to the active visual speed of processing training.

To facilitate rapid recruitment into the study, randomization stratification will not be performed. After 10 weeks, both groups will complete the assessments that were used at enrollment.

Research Methods and Procedures for Post SAH Memory Study

Recruitment and Screening:

Recruitment: Study participants will be recruited in the following ways:

- A. *Neurosurgery Clinic Setting:*

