 Those with a modified Rankin 0 or 1
 Baseline memory problem affecting daily life
 Home computer or tablet with internet access

Exclusion

Unable to read or speak English

Data Analysis:

Data will be analyzed by a Spearman rank-order correlation. Data will be compared by using the number of completed puzzles and the amount of time spent completing them with changes noted on the CLCE-24 and working memory questionnaires. The Spearman rank-order will be used to show a monotonic relationship with completing strategy orientated puzzle and reduction in memory symptoms.

Table of Expected Results

Testing	Baseline	Post Intervention	Controls
CLCE-24	Cognitive and Emotional complaints: 3.3	Cognitive and emotional complaints: 1	Cognitive and emotional complaints: 3
ADLQ	Total: 17/84 or 20%	Total: 10/84 or 11%	Total: 18/84 or 21%
Working Memory	Total: 34.5 Storage: 11 Attention: 14 Executive Function: 9	Total: 20 Storage: 6 Attention: 8 Executive Function: 6	Total: 32 Storage: 10 Attention: 14 Executive Function: 8

Estimated sample size: 108 subjects total.

For CLCE-24, a sample size of 50 patients per group (total of 100 patients) can provide 80% power to detect a difference of 2 in number of complaints between the two groups, with a significance level of 0.5 and using a two-sample t-test (two-sided). For the Working memory questionnaire, a sample size of 54 patients per group (total of 108 patients) will achieve 80% power to detect a difference of 12 points between the two groups, with a significance level of 0.5 and using a two-sample t-test (two-sided).

Data Collection:

Data will be collected at different time points in this study. Please refer to table 1 for further reference.

Week 1: Consent, enrollment, completion of three Redcap assessments and Lumosity assessments. Randomization. Intervention group will receive access to Lumosity and control will get access to crossword puzzles.

Weeks 2-9: Intervention group will be reminded to complete Lumosity games; active controls will be reminded to complete cross-word puzzles

Week 10: All subjects complete the three Redcap assessments, the Lumosity assessments. Study completed at this time.

Table 1.

Group	Week 1	Weeks 2-9	Week 10
Intervention			
CLCE24/Working memory/ADLs/Lumosity	X		x
Lumosity	x	x	X
Control			
CLCE24/Working memory/ADLs/Lumosity	X		X
Active control		x	X

*At 70 day assessment, patients will have a +/-10 day window to submit questionnaires.

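### The +/-10 day window lets the REDCap questionnaires be submitted from day 60, up to 10 days before the 10-week course ends, so some endpoint values may reflect an incomplete course

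*Combined protocol and SAP*

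**What the plan says.** The combined protocol and SAP describes the course length and the assessment time in several places.

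- **Course (Intervention group paragraph).** Participants "will undergo twenty training sessions over 10 weeks". A later paragraph of the Study Plan gives the amount in hours: "The recommended interaction would be 2 hours per week for 10 weeks for a total training time of 20 hours".
- **Assessment time (Study Plan, after the Active control group paragraph).** "After 10 weeks, both groups will complete the assessments that were used at enrollment".
- **Assessment time (Data Collection).** "Week 10: All subjects complete the three Redcap assessments, the Lumosity assessments. Study completed at this time". Table 1 still marks both programmes in week 10.
- **Window (footnote to Table 1).** "At 70 day assessment, patients will have a +/-10 day window to submit questionnaires".
- **Weeks before the assessment (Data Collection).** "Weeks 2-9: Intervention group will be reminded to complete Lumosity games; active controls will be reminded to complete cross-word puzzles".
- **Start of access (Data Collection, week 1, listed after consent, baseline assessments and randomization).** "Intervention group will receive access to Lumosity and control will get access to crossword puzzles".

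The documents do not say which event is day 0. They do not make submission depend on finishing the course, and neither Data Analysis section says how an early submission is handled. The footnote names questionnaires only; no window is given for the eight Lumosity assessments.

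**The concern.** A symmetric window is common for a follow-up visit. Here the nominal day coincides with the last day of the course, so the whole early half of the window lies inside the training period. A participant who submits on day 60 complies with the footnote while still being reminded to train, and does not comply with the statement that assessment follows the 10 weeks.

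The group comparison is meant to capture the effect of the full course. A questionnaire submitted early may capture only part of it, and because the study ends at this assessment, nothing later can replace that value. The window covers the CLCE-24 and the Working Memory questionnaire, the two outcomes in the sample size paragraph.

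There is a second, smaller consequence. The first Data Analysis section correlates the number of completed puzzles and the time spent on them with change on these questionnaires, and gives no cut-off date for counting usage. For an early submitter, training done after the outcome was recorded could be counted as exposure.

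**Working it through.** **Inputs from the documents.** Course: 20 sessions, 20 recommended hours, 10 weeks. Assessment: day 70, window 10 days either side. Sample size: 54 per group, 80% power, 12-point Working Memory difference, two-sided two-sample t-test. SD: 22.1, given for brain-injured people in the description of the Working Memory questionnaire.

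**Assumptions.** That SD is taken to be the one behind the 54. The significance level is taken as 0.05: the paragraph prints 0.5, but 0.5 gives 16 per group, whereas 0.05 reproduces the stated number. Benefit is assumed to build linearly with training time up to day 70; the documents do not say this.

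**1. The plan's own figures.**
- 10 weeks × 7 = 70 days, and 2 hours × 10 = 20 hours. Both agree with the text.
- n per group = 2 × (1.96 + 0.84)² × (22.1/12)² ≈ 53.2, rounded up to 54. The exact t-test calculation gives 54.2, and power at 54 per group is 79.8%. The plan is reproduced, with no margin.

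**2. The window against the course.**
- Earliest permitted submission: 70 − 10 = day 60, in week 9 (days 57 to 63).
- Share of the course elapsed: 60/70 = 85.7%.
- Sessions at the planned pace: 20 × 60/70 = 17.1, a shortfall of 2.9.

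**3. Effect on the Working Memory comparison.** Expected difference = 12 × mean share of the course completed. Power is from the two-sample t-test with 54 per group.

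For an even spread over days 60 to 80, half the submissions come before day 70 and are on average 5 days short. The mean shortfall is 0.5 × 5 = 2.5 days, and the mean share is 1 − 2.5/70 = 96.4%.

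| Submission pattern | Mean share | Difference | Power |
|---|---|---|---|
| None before day 70 | 100% | 12.0 | 79.8% |
| Even over days 60 to 80 | 96.4% | 11.6 | 76.9% |
| Half on day 60, half on or after day 70 | 92.9% | 11.1 | 73.8% |
| All on day 60 | 85.7% | 10.3 | 66.9% |

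**4. The undefined day 0, kept separate.** Suppose day 0 is consent and access comes 7 days later (assumption).
- Assessed exactly on day 70: 63/70 = 90% of the course, 10.8 points, 71.1% power.
- Assessed on day 60: 53/70 = 75.7%, 9.1 points, 56.2% power.

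Of the 17 missing days in the second case, 7 come from the start date and 10 from the window. In this scenario the window accounts for the fall from 71% to 56%; the fall from 80% to 71% comes from the undefined start.

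**The case against.** The case for leaving the plan as it is has several parts.

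- **Early submission is allowed, not shown.** The 20 hours are a recommendation, a participant could finish the sessions ahead of pace, and nobody knows how many would submit before day 70. The documents also do not say when the post-treatment survey link is sent, so the practical opening may be later than day 60. This stands: the values *may* reflect an incomplete course, and no more can be said.
- **The large power losses are extreme cases.** Power of 67% needs every participant at the early edge together with linear benefit. Power of 56% also needs a late start that the window does not cause. This stands, and neither figure is the expected effect.
- **The arms are treated alike.** A reader might infer that participants who know their arm will choose different submission days, biasing the comparison. The window is the same for both arms, the control is active, and nothing in the documents points to different timing. Table 1 marks Lumosity but not the control programme in week 1, but the text gives both arms access that week. Differential timing is possible, but it is not established.
- **Usage is recorded.** The planned Spearman correlation uses puzzles completed and time spent, so a shortfall could be seen. That helps interpretation, but it does not correct the comparison between groups.
- **A narrower window could cost follow-up.** These participants are selected for memory problems. If closing the window at day 80 lost 4 of 54 per arm, power at 50 per arm would be 76.7%, which cancels the roughly 3-point gain. This is a fair objection to halving the window. It does not apply to one of the same width that opens later.

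**Conclusion.** The point holds in a limited form. The documents permit the three REDCap questionnaires, including both outcomes that size the trial, to be submitted up to 10 days before the course ends. That contradicts the statement that assessment follows the 10 weeks, and no later assessment exists.

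The expected effect is modest dilution of the group difference: about 0.4 of 12 points and about 3 percentage points of power. This rests on an even spread of submissions, linear benefit, an SD of 22.1 and a two-sided level of 0.05. At most 14% of the course is missed because of the window.

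Two stronger readings are not supported. One is that endpoint values will measure an incomplete course; the text only allows it. The other is that every post-treatment measure is affected; the footnote is limited to questionnaires and leaves the Lumosity assessments without any stated window.

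This is a cheap improvement, not a threat to the trial's validity.

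**What to change.** - Define day 0 as the day programme access is given, in both arms.
- Open the questionnaires no earlier than day 70 and put the window on the late side only, for example day 70 to day 90, which keeps the 20-day width. Schedule the REDCap survey so that it cannot be submitted earlier.
- State the same window for the Lumosity assessments.
- Reconcile the Study Plan's statement of assessment after the course, the week 10 entry under Data Collection, and Table 1, which still marks training in that week.
- Count usage for the Spearman analysis only up to the date the questionnaires are submitted.

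**Cost.** A few sentences and one survey-scheduling setting. With a window to day 90, some assessments fall up to 20 days after training ends, so timing still varies. Closing at day 80 would limit that, but it halves the window and may need more reminders.

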What may be more helpful to these patients is a resource that is more convenient, less costly, and yet effective in alleviating the types of memory difficulties oftentimes seen after SAH. Online-based cognitive interventions may represent one such option. Online cognitive interventions are becoming increasingly available and offer easier access, easier delivery, and the ability to track and analyze performance on these exercises in an automated fashion. Administering exercises using paper and face-to-face encounters requires significant time and effort to deliver. *Lumosity*, one such program, claims to bolster cognitive performance by regular engagement in various games and mental exercises. It has been studied in patients with cancer related and traumatic brain injury patients. Significant improvements in processing speeds, mental flexibility and memory have been reported. No similar interventions have been reported in patients within the first few months after an aneurysmal SAH. Given the unique characteristics of many patients who survive a ruptured brain aneurysm, and the feasibility of using online cognitive interventions, we sought to evaluate its effect through a clinical randomized control study.

Study Plan:

Our study aims to determine if periodic online cognitive exercises improve memory function in ruptured cerebral aneurysm patients with disabling baseline memory deficits within the first 12 months. Eligible subjects will be physically independent but have a self-reported disabling memory deficit within the first year of their ruptured cerebral aneurysm. Screening will be determined by a series of questions either in person or over the telephone. All enrolled subjects will complete memory assessments to determine baseline function.

Assessments:

Redcap administered assessments:

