 1. Study staff will be utilizing REDCap’s randomization tool. The randomization tool has been formatted to randomize patients into one of two groups, “Lumosity” or “active control”. **Stratification factors will include age (<50, 50 or older), gender, level of education (greater than high school education or not) and time since rupture of the aneurysm (<6 months or 6-12 months).** Randomization by the study staff will occur when the participant completes the demographic survey. This tool will help the study better implement a defined randomization model and allow the study staff to randomize participants easily.

[figure not shown]
Screen shots of the Project’s Randomization Tool:

b. Delivery of patient surveys

1. Surveys (CLCE-24, Working Memory, and Activities of Daily Living ADL Scale) will be sent to participants via the REDCap system. Study participants will be able to complete all surveys and submit them online. Individual emails are sent out to each person in the study. The email will contain brief instructions about completing the survey and a secured link to their individual survey queue.

Screen shot of the Survey Queue:

c. Collection of Survey Responses:

1. The REDCap database will alert the study team on which surveys were and were not completed by specific participants. The study staff will be able to send reminders to those who have not yet completed all the required surveys in their queue.

Screen shot of the participant list:

Participant List belonging to [Initial survey] "Information about you" Remove all participants

Displaying 1 - 7 of 7 Add participants Compose Survey Invitations Export list

Email	Participant Identifier	Responded?	Invitation Scheduled?	Invitation Sent?	Link	Survey Access Code	Survey Queue
[No email listed]	Disabled		-				remove
[No email listed]	Disabled		-				remove
[No email listed]	Disabled		-				remove
[No email listed]	Disabled		-				remove
[contact]	Disabled		-		-	-	
[contact]	Disabled		-				remove
[contact]	Disabled		-		-	-	

d. Data Export

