Data Analysis: The primary analysis should be comparisons between the two groups for the outcome measures. T test or Mann-Whitney test can be used for comparisons and regression analysis may be performed with adjustment of baseline characteristics.

Questionnaires

For the CLCE-24, Working Memory and Activities of Daily Living Questionnaire, please see Appendix A.

Processes and controls to ensure study integrity

A key differentiator in this study is the use of online consent, data acquisition and data analysis. A concern for data being collected in this fashion concerns sampling bias and construct validity. One might think that support groups and online social networks may not capture data from patients who are older and not as familiar with technology. However, as social media improves its user interface, greater numbers of older users are being engaged. We believe *Lumosity* represents one such solution to address this concern. With regard to construct validity, we have included a series of questions we will administer over the phone in the event subjects are not actual patients of our practice for whom we have been able to review the relevant history, physical examination and imaging findings. Users of targeted social network groups are likely to be a self-selected motivated group of individuals. The likelihood that individuals without a diagnosis of brain aneurysm would be a part of this targeted social network and participate in the study seems unlikely. We hope that the relatively larger size of the dataset relative to previously published single-center series can overcome the effect any erroneous outliers may have on biasing the data.

Suitability of investigator(s) and institution

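### Nothing commits the primary group comparison to each participant's own Week 1 score, so precision that the trial already collects may go unused

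*Combined protocol and SAP*

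**What the plan says.** The second Data Analysis paragraph (after Table 1) defines the primary analysis: "The primary analysis should be comparisons between the two groups for the outcome measures". On method it adds: "T test or Mann-Whitney test can be used for comparisons and regression analysis may be performed with adjustment of baseline characteristics". It does not name the baseline characteristics, and it does not say whether the outcome measure is the Week 10 score or the change from Week 1.

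Baseline scores will exist. The Study Plan says "All enrolled subjects will complete memory assessments to determine baseline function", and the Data Collection schedule and Table 1 place all three REDCap questionnaires at Week 1 and Week 10 in both groups.

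The Estimated sample size section rests on an unadjusted two-sample t test. For Working Memory, 54 per group "will achieve 80% power to detect a difference of 12 points between the two groups". The significance level is printed as 0.5.

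Under Participant Randomization the factors are listed: "Stratification factors will include age (<50, 50 or older), gender, level of education", followed by time since rupture. No baseline outcome score is among them. The paragraph that closes the description of the two arms says instead that there will be no stratification.

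**The concern.** A t test or Mann-Whitney test on Week 10 scores takes no account of where each participant started. In a questionnaire given twice to the same person, the first score is usually a strong predictor of the second, and regressing on it removes that part of the variation from the treatment comparison. As written, the plan can be followed to the letter without ever using the Week 1 score in the group comparison. It also leaves the choice of whether to adjust, and for what, until after the data are seen. At stake are the width of the confidence interval and the power obtained from 108 participants, and whether the estimate that counts is fixed in advance.

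**Working it through.** **Inputs from the protocol**
- Difference for Working Memory: 12 points (Estimated sample size). It equals the expected control total minus the expected treated total, 32 − 20 (Table of Expected Results).
- SD: 22.1, the cross-sectional SD for people with brain injury (Assessments, Working memory).
- 54 per group and 80% power (Estimated sample size).

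**Assumptions, not in the documents**
- Two-sided significance level 0.05.
- The same SD in both arms.
- Correlation r between Week 1 and Week 10 scores of 0.3, 0.5 or 0.7.

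**Step 1: reproduce the plan's figure.** n per group = 2(z₁₋α/₂ + z₀.₈)² SD² / d².
- At 0.05: 2 × (1.960 + 0.842)² × 22.1² / 12² = 53.2, rounded up to 54. This matches.
- At the printed 0.5: 2 × (0.674 + 0.842)² × 22.1² / 12² = 15.6, rounded up to 16. This does not match.

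The sizing is therefore an unadjusted comparison at 0.05 with the full cross-sectional SD. By noncentral t, power at 54 per group is 79.8%.

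**Step 2: adjust for the Week 1 score.** The residual SD is 22.1 × √(1 − r²), the SE of the difference is residual SD × √(2/54), and the model uses one more degree of freedom.

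| Analysis | Residual SD | SE | Power at 54 per group | Equivalent increase in participants, 1/(1 − r²) − 1 |
|---|---|---|---|---|
| Unadjusted | 22.1 | 4.25 | 79.8% | – |
| ANCOVA, r = 0.3 | 21.1 | 4.06 | 83.4% | 10% |
| ANCOVA, r = 0.5 | 19.1 | 3.68 | 89.8% | 33% |
| ANCOVA, r = 0.7 | 15.8 | 3.04 | 97.5% | 96% |

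**Step 3: dropout.** The plan states no allowance. As an illustration, assume 20% loss, leaving 43 per group (54 × 0.8 = 43.2). Unadjusted power is then 70.2%. With ANCOVA it is 74.2%, 82.0% or 93.6% at r = 0.3, 0.5 or 0.7.

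**Step 4: CLCE-24.** No SD is given. Solving the same formula for 50 per group and a difference of 2 gives an SD of about 3.57. The factor 1 − r² applies here too: 50 × 0.91, 50 × 0.75 and 50 × 0.51 give 46, 38 and 26 per group after rounding up.

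**The case against.** The plan permits an adjusted regression, and a Week 1 score can fairly be read as a baseline characteristic. The t test and Mann-Whitney are themselves only tests that can be used. That stands: the fault is missing prespecification, and a reader who inferred that the plan excludes the baseline score would be going too far.

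The unadjusted test is valid under randomisation and reaches about the plan's own power target. That also stands. The loss is a forgone gain whose size depends on r, and at r = 0.3 it is only 3.6 percentage points of power.

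A reader might infer that chance imbalance in Week 1 scores biases the unadjusted result, as a second harm. It does not. If the Week 1 SD is also 22.1 (assumed), the arms have a 24% chance of differing by more than 5 points at baseline. At r = 0.5 such a difference shifts the estimate by 0.5 × 5 = 2.5 points, which is inside one standard error (4.25). That variation is already part of the unadjusted standard error, so it is the same variance seen from another side.

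A reader might also infer that the plan intends to compare change scores between groups. The phrase "with changes noted on the CLCE-24 and working memory questionnaires" belongs to the Spearman analysis of puzzle count and time. No section proposes change from baseline for the group comparison, although the wording leaves the form of the outcome open.

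**Conclusion.** The point holds as an inexpensive improvement that the plan should adopt. The primary comparison is valid but not tied to the Week 1 score, and its adjustment is optional and unspecified. For Working Memory, naming the adjustment would lift power by about 4, 10 or 18 percentage points at r = 0.3, 0.5 or 0.7. This assumes SD 22.1, a 12-point difference, two-sided 0.05 and 54 per group analysed. The direction is secure for any non-trivial correlation; near r = 0 adjustment costs a degree of freedom and gains nothing. The size is uncertain, because the documents do not give r and the SD comes from a general brain-injury sample, whereas this trial enrols only people with modified Rankin 0 or 1 and a memory problem.

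The documents do not support calling the trial underpowered on its own inputs, nor calling the unadjusted estimate biased.

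**What to change.** In the second Data Analysis paragraph, replace the sentence on tests with wording such as: *For each questionnaire, the Week 10 score will be compared between randomised groups by linear regression (ANCOVA) on treatment group and the participant's own Week 1 score on the same instrument, with the stratification factors added if they are used in randomisation. The adjusted mean difference will be reported with its 95% confidence interval.*

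Keep the unadjusted t test or Mann-Whitney as a sensitivity analysis. The rank test is useful for CLCE-24, a count expected to fall to 1 in the treated arm and so likely to be skewed.

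Keep the total at 108. Do not add a statement that the existing power figure is now conservative. With 20% loss and r = 0.3, adjusted power is 74.2%, below 80%, and the power sentence still carries the printed 0.5, which needs its own correction.

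Cost: one or a few degrees of freedom and a simple prespecified rule for a missing Week 1 score, such as mean imputation of the covariate. No new data, visits or participants are needed. This change does not settle which questionnaire is primary or whether randomisation is stratified; those need separate decisions.
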